**11.8 \* Data Analysis**

Describe method(s) of data analysis. Include the role of external collaborators as appropriate.

As per recommended by the food and drug administration (17), the hemagglutination inhibition (HI) antibody assay has been used to assess vaccine activity and may be appropriate for the evaluation of the pandemic influenza vaccine. Appropriate endpoints may include: 1) the percentage of subjects achieving an HI antibody titer  $\geq 1:40$ , and 2) rates of seroconversion, defined as the percentage of subjects with either a pre-vaccination HI titer  $< 1:10$  and a post vaccination HI titer  $> 1:40$  or a pre-vaccination HI titer  $\geq 1:10$  and a minimum four-fold rise in post-vaccination HI antibody titer. Previous study have built models using both HAI and neutralization assays to determine vaccine responsiveness.

The RNA-seq analysis will be run with the help of the Genome resource center as well as the expertise of [name] listed as a collaborator of this project.

**11.9 \* Explain the rationale for the choice of statistical measures and the number of subjects proposed for the study, including the power calculations when applicable.**

Since no preliminary data is available to estimate the percentage of participants achieving a determined level for the HI antibody titer and the rate of seroconversion for each group (healthy volunteers and metabolic syndrome participants) we provide an estimation of the minimum effect size for the sample size selected is able to detect. For a sample size of 40 participants, 20 at each group, a 95% significant Chi-square test will be able to detect an effect size equal or larger than 0.56 with 0.8 power. It means that a Chi-square test will be able to detect independence between groups if the distance between the observed odd ratio is larger than 1.56.

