**Statistical Analysis**

To compare the means of antibody titers between groups (healthy volunteers and metabolic syndrome participants) a t-test at 95% significance level will be performed if the data follows a normal distribution, otherwise a non parametric Wilcoxon-Mann-Whitney test will be used.

A Chi-square test at 95% significance level will be used for the comparison of percentage of participants achieving a determined level for the HI antibody titer and rates of seroconversion. On that case if any observed frequency is smaller than 5 Fisher exact test will be used instead of Chi-square.

Expression values will be modeled using mixed-effect models, with group as fixed factor, and a random effect for each participant. FCHs for the comparisons will be estimated, and hypothesis testing conducted.

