**12.6 Vulnerable Populations**

Indicate whether any of the following populations will be included in the study:

- Children  
 Pregnant Women  
 Cognitively Impaired Persons  
 RU Employees  
 RU Students  
 Fetal Tissue or Embryonic Stem Cells  
 Induced Pluripotent Stem Cells  
 Other:

If you checked any of the above, give a brief explanation of the need to use these particular individuals:

Special precautions will be used in recruiting employees of the Rockefeller University to minimize the possibility of undue influence. Rockefeller University employees will be made aware of the study through flyers rather than directed presentation to selected groups. Subjects will be reassured that refusal to participate in the study will not affect their studies or employment in any way

If the subject is a Rockefeller University employee, does she/he work within the Laboratory of the Principal Investigator or Co-Investigator(s)?

- Yes  
 No  
 N/A

If the subject is a Rockefeller University student, does she/he work within the Laboratory of the Principal Investigator or Co-Investigator(s)?

- Yes  
 No  
 N/A

**12.7 \*What is the total number of evaluable participants you plan to enroll at Rockefeller University Hospital over the course of the entire study?**

40

**12.8 \* What is the total number of participants who will need to sign consent at Rockefeller University Hospital over the course of the entire study to result in the desired number of evaluable subjects?**

100

**12.9 \* What is the total number of participants you plan to sign consent at Rockefeller University Hospital in the next year?**

100

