## 16.0 Recruitment and Advertising

**For assistance consult CRSO to create a robust Recruitment Plan see Help.**

### 16.1 \* What is the plan for recruitment?

**Overview:**

The CRROSS will prescreen up to 100 volunteers in order to enroll 20 with a metabolic syndrome and 20 healthy controls to achieve the goal of 40 evaluable participants at study completion. Healthy controls will be age matched (+/-5 years) and gender matched to the metabolic syndrome participants.

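### Section 11.9 presents an odds ratio above 1.56 as detectable with 20 per group; power there is below 11%, 80% power needs about 6.6 or more, and the 0.56 behind it does not follow from its inputs

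*Combined protocol and SAP*

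**What the plan says.** Section 11.9 explains that no preliminary response rates exist, so the sample size is taken as given and the detectable effect is worked out from it: "we provide an estimation of the minimum effect size for the sample size selected is able to detect". The design is stated as "For a sample size of 40 participants, 20 at each group", and the result as "a 95% significant Chi-square test will be able to detect an effect size equal or larger than 0.56 with 0.8 power". The next sentence interprets this figure for the reader: the test will "detect independence between groups if the distance between the observed odd ratio is larger than 1.56".

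The effect-size index, the degrees of freedom and the response rates are not given, and no step from 0.56 to 1.56 is shown.

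The Statistical Analysis text after section 11.9 applies the test to the proportion reaching a set HI titer and to seroconversion: "A Chi-square test at 95% significance level will be used for the comparison of percentage of participants achieving a determined level". It adds a switch: "if any observed frequency is smaller than 5 Fisher exact test will be used instead of Chi-square". Section 12.7 puts the number of evaluable participants at 40, and section 16.1 sets recruitment "to achieve the goal of 40 evaluable participants at study completion", so 20 per group can be taken as the analysed number.

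**The concern.** The figure 1.56 equals 1 + 0.56. No standard effect-size index for a 2x2 table becomes an odds ratio by adding 1. An odds ratio of 1.56 is a modest association (14/20 against 12/20), and 20 per group would not be expected to find it. The 0.56 also looks too large for Cohen's w with one degree of freedom and N = 40.

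The two errors run in opposite directions. An effect size of 0.56 understates what the design can detect; an odds ratio of 1.56 greatly overstates it. The second matters more, because it is the sentence that tells the reader what the number means. Anyone relying on it would think the study sensitive to modest differences in response, and could take a non-significant binary comparison as evidence that metabolic syndrome makes no difference.

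**Working it through.** **Inputs.** N = 40, 20 per group, power 0.80 (section 11.9); 40 evaluable (sections 12.7 and 16.1), so no dropout deduction; 5% two-sided chi-square with the Fisher switch (Statistical Analysis). Two groups by yes/no gives df = 1. Response rates are not stated, so results are taken over all rates from 1% to 99%. The index is not named; Cohen's w is assumed first, then h.

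**1. Can 0.56 be reproduced?** Power = P(noncentral chi-square with df = 1 and noncentrality N·w² > 3.841).

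- For 80% power: N·w² = (1.960 + 0.842)² ≈ 7.85, so w = √(7.85/40) = **0.443**.
- At w = 0.56: N·w² = 40 × 0.3136 = 12.54, and power is **94.3%**.
- Cohen's h with 20 per group: (1.960 + 0.842)/√10 = **0.886**.

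So 0.56 fits neither index. It appears only with inputs that are not this design: N = 25 (0.560), N = 20 at alpha 0.10 (0.556), or roughly df = 5 (0.566).

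**2. Does 0.56 correspond to an odds ratio of 1.56?** For equal groups, w = |p1 − p2| / (2√(p̄(1 − p̄))). With symmetric rates, w = 0.56 means 78% vs 22%, and the odds ratio is (0.78/0.22)² = **12.6**.

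**3. 1.56 as an observed odds ratio.** For 14/20 vs 12/20 the odds ratio is (14/6)/(12/8) = 1.556. Here w = 0.10/(2√(0.65 × 0.35)) = 0.105, chi-square = 40 × 0.105² ≈ 0.44, and **p = 0.507**. The mirror table, 8/20 vs 6/20, gives the same. An odds ratio alone does not fix p, but tables with odds ratios from 1.49 to 1.62 all give p between 0.49 and 0.63. Even with non-integer counts the smallest p at 1.56 is 0.484.

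Across all tables with no empty cell, the smallest observed odds ratio reaching 5% is:

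- Pearson: **4.0** (10/20 vs 4/20, p = 0.047);
- planned rule: **4.33** (13/20 vs 6/20, p = 0.027). The 10 vs 4 table has a cell below 5, so Fisher applies and gives p = 0.096.

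**4. 1.56 as a true odds ratio.** Noncentral chi-square power is greatest near 44.5% vs 55.6%: w = 0.111, N·w² ≈ 0.49, power 10.8%. The exact figures enumerate all 21 × 21 tables, with Pearson uncorrected.

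| | Noncentral chi-square | Exact Pearson | Exact, planned rule |
|---|---|---|---|
| Maximum power, true odds ratio 1.56 | 10.8% | 10.5% | 8.8% |
| Maximum power, true odds ratio 2 | 19.2% | 18.2% | 16.3% |
| Smallest true odds ratio with 80% power | 6.7 | 6.6 | 6.7 |

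The first two rows are maxima and the last is a minimum over response rates, so the missing rates cannot rescue the claim. By the normal approximation, 80% power at a true odds ratio of 1.56 needs at least 319 per group.

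**5. What the design can detect.** At 72% vs 28%: w = 0.44/(2 × 0.5) = 0.44, odds ratio (0.72/0.28)² = 6.61, power 79.5% (noncentral), 80.1% (exact Pearson), 79.4% (planned rule).

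**The case against.** The strongest defence has four parts.

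- **The index is unnamed.** The statement that 0.56 should be 0.44 holds only if Cohen's w is meant. This stands as a condition. What is shown without it is that 0.56 fits neither w nor h for this design. That the authors added 1 is likewise an inference from 1.56 = 1 + 0.56.
- **The sentence is garbled.** It speaks of detecting independence and of a distance involving a single odds ratio, so its intended meaning is uncertain. That is true, but it fails both as an observed and as a true odds ratio, and nothing elsewhere in the document corrects it.
- **Nothing was built on the figure.** N was fixed first, the planned tests do not use 1.56, and the titer comparison by t-test or Wilcoxon lies outside this calculation. All of this stands and limits the harm to what the binary comparisons can be said to show. It does not excuse the figure: section 11.9 asks for the power rationale, and no other is offered.
- **6.6 is the favourable case.** This is right. At w = 0.443 the odds ratio is about 7.7 for 85% vs 42%, 9.3 for 90% vs 49% and 14.2 for 95% vs 57%. In the first two cases power under the planned rule falls slightly, to 77.7% and 76.3%. So 6.6 has to be read as a floor, which makes the gap from 1.56 wider.

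**Conclusion.** The concern holds. The claim attached to 1.56 is false on either reading, and the error is in the favourable direction: 1.56 stands where about 6.6 or more belongs, roughly a fourfold overstatement of sensitivity on the odds-ratio scale. At least 89% of such studies would miss a true odds ratio of 1.56. This rests on 20 evaluable per group and a two-sided 5% test, and on no assumption about response rates.

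The 0.56 is a second, conservative error: 0.44 if Cohen's w with df = 1 is meant, and no match for Cohen's h (0.89) either. Correcting it does not rescue the odds ratio. No test, enrolment figure or procedure is invalidated. Because this is the plan's only sample-size justification, it must be corrected.

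**What to change.** In section 11.9, replace the sentence giving the effect size of 0.56 and the sentence giving 1.56 with:

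> With 20 evaluable participants per group, a two-sided 5% chi-square test has about 80% power to detect an association of w = 0.44, for example 72% vs 28% (odds ratio about 6.6; a larger odds ratio is needed when response rates are nearer 0% or 100%). Smaller differences, including odds ratios of 2 or less, cannot be reliably detected, and a non-significant result will not be taken as evidence of no difference.

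The figure 1.56 should not appear in any form. The last clause goes beyond arithmetic, but it follows from the power figures and guards against the misreading that the present text invites.

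The cost is two sentences and a much less favourable stated sensitivity. No participants are added and conduct does not change.

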**Statistical Analysis**

To compare the means of antibody titers between groups (healthy volunteers and metabolic syndrome participants) a t-test at 95% significance level will be performed if the data follows a normal distribution, otherwise a non parametric Wilcoxon-Mann-Whitney test will be used.

A Chi-square test at 95% significance level will be used for the comparison of percentage of participants achieving a determined level for the HI antibody titer and rates of seroconversion. On that case if any observed frequency is smaller than 5 Fisher exact test will be used instead of Chi-square.

Expression values will be modeled using mixed-effect models, with group as fixed factor, and a random effect for each participant. FCHs for the comparisons will be estimated, and hypothesis testing conducted.

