To support our hypothesis, several studies have demonstrated that during the 2009 influenza H1N1 pandemic, obesity was associated with more severe infection and death (6, 14). The mechanism is likely immune mediated but has not been determined yet (15). Also, it has been reported that obese people might be less protected by influenza vaccination (7). The area of systems biology has considerably contributed to a better understanding of vaccine efficacy (10, 16). Gene expression studies using peripheral blood can predict vaccine response to influenza (10, 11). High vaccine response correlates with the expression of interferon signaling (genes like STAT1, IRF9) and antigen processing and presentation. To test our hypothesis, we contacted the authors of a study published in Cell in 2014 (12) and obtained the BMI of the patients. The study demonstrated the ability to predict the influenza vaccine response using several parameters. We focused on the immune response based on antibody titers and the gene expression profile at D0 and D1. We separated the individuals in 2 groups: one group of lean (BMI<25) and one group overweight and obese (BMI>25). The two groups contained 25 and 17 individuals respectively. We observed a trend towards an inverse correlation of the immune response to influenza vaccine with increasing BMI. Also, we analyzed the differential gene expression profile between D0 and D1 between the two groups. JUN Kinase, Stat1 and IRF1 were among the most up-regulated genes in the lean group but not in the overweight and obese group. When comparing the two groups using ingenuity pathway analysis, the role of PKR in interferon response, Toll like receptor signaling, Natural killer cell signaling were more activated in the lean group compare to the overweight and obese group. These results indicated that the innate immune response induced by the vaccine might be attenuated in the overweight and obese group. BMI was the only factor used for this analysis and we did not have access to any metabolic marker. Obesity is not necessarily associated with an unhealthy metabolic status. Therefore, we would now like to focus on metabolic syndrome as it better correlate with an unhealthy metabolic status. Our aim is to determine if metabolic syndrome attenuates the immune protection induced by the vaccine and establish the molecular mechanism of antiviral immune deficiency associated with metabolic syndrome. We would like to know if differences between people with and without metabolic syndrome can be seen at the molecular level and correlate with differences in antibody titers. We believe our study will contribute to 1/ better understand vaccine efficacy 2/ establish if the low-grade chronic inflammation associated with metabolic syndrome impacts the systemic immunity against viral infection.

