**11.7 \* Methods and Procedures**

Please provide a description of the laboratory and clinical analyses and procedures that will be performed. Include the role of external collaborators and consultants when appropriate.

Participants will be seen at Rockefeller University as outpatients. There will be two (2) cohorts, namely those with the metabolic Syndrome who have not been treated and healthy volunteers.

The Metabolic Syndrome will be determined according to the NHLBI Guidelines.

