**SCREENING VISIT #1**

Consent

Medical history

Physical examination including height and weight to determine BMI, and waist circumference

Vital Signs - If the initial blood pressure is above 150/90 mmHg upon arrival to the OPRC, a second B/P will be taken by the LIP during the screening process. The average of the two readings will be the enrollment criterion.

POCT - HIV

POCT - urine pregnancy test

Labs: HbA1c - (1) 3.0 ml lavender tube

Hepatitis Panel - (1) 8.5ml SST marble top tube

Comprehensive metabolic & CRP - (1) 8.5 ml SST marble top tube

CBC - 3 ml lavender top tube

Gene expression - (3) 2.5ml Pax RNA tube (total 7.5ml).

Influenza A & B antibodies - (1) 10ml red top tube

Total blood volume to be drawn for screening visit 1 = 40.5ml .

Instructions to return fasting for 8 hours prior to the next visit.

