**SCREENING VISIT #2 (within 2 weeks of screening visit #1)**

Adverse event assessment

Fasting Labs: Glucose, lipids and triglycerides) - (1) 3.5ml gold top tube

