**Order Number    Criteria**

1                      Currently undergoing treatment for the metabolic syndrome

2                      Blood Pressure > 150/90

- 3 NSAIDs and/or Aspirin ingestion within the last 14 days
- 4 Hepatitis A, B and C
- 4 Self-reported history of any active autoimmune diseases
- 5 Self-reported ingestion of statins within the last 3 months
- 6 Self-reported antibiotic use within the last 3 months
- 7 Anti-inflammatories including biologics and corticosteroids within last 3 months( nasal spray and topical applications are OK)or Omega 3 Fatty Acids.
- 8 Self-reported hx of cancer treatment within the last year
- 9 Allergy to eggs
- 10 History of Guillain-Barre syndrome
- 11 Pregnant ( determined by POCT at Screening visit #1 and Study visit #1).
- 12 HIV positive
- 13 Self-reported history of receiving the flu vaccination after June 1, 2016.
- 14 Any self-reported infection in the week of the visit except the first two visits (Screening visit 1 and Screening visit 2) and the last visit (Study visit #5) that could be rescheduled.
- 15 Any medical, psychological or social condition that, in the opinion of the Investigator, would jeopardize the health or well-being of the participant during any study procedures or the integrity of the data.

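### The between-group titre comparison gives the pre-vaccination titre no role, so in non-randomised cohorts an existing titre difference can carry into the result

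*Combined protocol and SAP*

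**What the plan says.** Under Statistical Analysis (section 11.9), the means of antibody titres in the two groups are compared: "a t-test at 95% significance level will be performed if the data follows a normal distribution", with a Wilcoxon-Mann-Whitney test otherwise. No covariate, change score or fold rise is mentioned, and neither the visit nor the scale of the titre is given. The only model in the plan is the mixed model for gene expression, which does not cover titres.

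Five other places bear on this:

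- **Aim (11.1 Overview):** "Our aim is to determine if metabolic syndrome attenuates the immune protection induced by the vaccine".
- **Group formation (11.7 Methods and Procedures):** "There will be two (2) cohorts, namely those with the metabolic Syndrome who have not been treated and healthy volunteers".
- **Matching (16.1, recruitment overview):** "Healthy controls will be age matched (+/-5 years) and gender matched to the metabolic syndrome participants".
- **Prior exposure (12.12 Exclusion Criteria):** the relevant exclusion is "Self-reported history of receiving the flu vaccination after June 1, 2016". Vaccination in earlier seasons is neither restricted nor matched.
- **Baseline data:** Screening Visit #1 (11.7) lists "Influenza A & B antibodies - (1) 10ml red top tube", and the same tube is drawn at Day 28 and Day 90. The seroconversion definition in 11.8 needs a pre-vaccination HI titre, since one of its two routes is "a minimum four-fold rise in post-vaccination HI antibody titer".

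**The concern.** A post-vaccination titre combines antibody already present with antibody raised by the vaccine. The stated aim concerns the second part. In a randomised trial the first part would balance on average. Here the groups are defined by disease status, and nothing in the design makes their pre-vaccination titres equal. Age matching may balance some exposure history, and the June 2016 cut-off applies to both cohorts, but neither ensures balance.

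If the cohorts start at different levels, an unadjusted test on post-vaccination titres can report that difference as an effect of metabolic syndrome on vaccine response. If the metabolic-syndrome cohort starts higher, the test can hide a real deficit. Antibody titre is the primary outcome (11.5), so this affects the main result.

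**Working it through.** The plan gives no figure for this comparison to reproduce. Its only power statement concerns the chi-square test.

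**Inputs from the documents:** 20 per group (11.9); 95% significance level, read as two-sided 5%.

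**Assumed, because the documents give no value:** within-group SD of log2 titre = 1 before and after vaccination; normal data; true baseline difference d (in SD units) of 0.5, with 0.25 as a milder case; pre/post correlation r of 0.3, 0.5 and 0.7; baseline measured without error.

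The standard error of a difference in means is √(2/20) = 0.316. Rejection rates for the t-tests come from the noncentral t with 38 df. Those for ANCOVA (baseline as the only covariate) come from simulation.

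**Null A: no group effect at a given baseline titre.**

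- Post-only t-test: expected difference r·d, so noncentrality r·d/0.316. For d = 0.5 and r = 0.5 this is 0.25/0.316 = 0.79, giving 12%.
- Fold-rise t-test: expected difference (1−r)·d in size, SD of change √(2(1−r)), so noncentrality d·√((1−r)/2)/0.316. For d = 0.5 and r = 0.3 this is 0.5 × 0.592/0.316 = 0.94, giving 15%.
- ANCOVA: no bias under this null.

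**Null B: equal mean log fold rise in both cohorts.**

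- Post-only t-test: the whole baseline difference carries over, so noncentrality is 0.5/0.316 = 1.58 at every r, giving 34%.
- Fold-rise t-test: no bias.
- ANCOVA: expected bias (1−r)·d, which is 0.35, 0.25 and 0.15 SD for d = 0.5.

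Rejection rates at d = 0.5, for r = 0.3 / 0.5 / 0.7:

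| Analysis | Null A | Null B |
|---|---|---|
| Post-only t-test | 7.5% / 12% / 19% | 34% / 34% / 34% |
| ANCOVA on baseline | about 5% | 19% / 14% / 9.5% |
| Fold-rise t-test | 15% / 12% / 9% | 5% |

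With no imbalance all three hold 5%. At d = 0.25 under null A, the post-only t-test rejects 5.6%, 7% and 8%. The Wilcoxon test under null A is within 2 points of the t-test.

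**Hidden effect.** Suppose the true deficit at a given baseline is 0.8 SD and the metabolic-syndrome cohort starts 0.5 SD higher. The post-only difference shrinks to 0.8 − 0.5r, that is 0.65, 0.55 and 0.45 SD. Power of the t-test falls from 69% to about 52%, 40% and 28%. ANCOVA keeps about 69%, 77% and 91%.

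**Precision with no imbalance.** For a 0.8 SD effect, power is 69% for the t-test and about 72%, 80% and 92% for ANCOVA at r = 0.3, 0.5 and 0.7. At r = 0 it is slightly lower than the t-test (66–68% with age and sex also in the model).

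**Baseline noise.** Screening Visit #2 is "within 2 weeks of screening visit #1", and Day 0 follows within one month with a one-week window. The screening tube can therefore precede vaccination by about 14 + 30 + 7 = 51 days. If baseline reliability were 0.6 and d = 0.5, ANCOVA under null A would reject 5–8% where r is the correlation with the true baseline. Where r is the observed correlation, it would reject about 6%, 7% and 12%, against 9%, 17% and 29% for the t-test.

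**The case against.** The strongest objection is that the choice of null settles which method looks good. ANCOVA holds 5% under null A by construction. In non-randomised cohorts, equal mean fold rise is an equally reasonable null, and under it ANCOVA is the biased method. This stands. A reader might infer that a fold-rise comparison would fail too, or that ANCOVA is the only valid analysis. Neither follows, because the two methods answer different questions. What survives is narrower: the post-only test exceeds 5% under both nulls, whereas each alternative holds 5% under one.

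Second, the titre variable is undefined, so fold rise may be what was meant. The text does not exclude that, and the post-only figures apply only if post-vaccination titres are compared. The omission is still a gap, because the reader cannot tell which comparison is planned.

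Third, seroconversion already refers to each participant's own baseline and has its own planned test. It would be wrong to say that the plan ignores baseline altogether. But seroconversion is a separate, dichotomised comparison and does not repair the titre test.

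Fourth, attained titre is a legitimate question in itself: section 11.3 concerns risk of more severe infection, and 11.8 uses a 1:40 threshold. Metabolic status may also have shaped earlier immunity, so baseline could lie on the causal path. That is a reason to keep the unadjusted comparison as a supporting analysis and to state the estimand.

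Finally, no document shows that the cohorts will differ at baseline. This is correct, and it limits what can be said about size.

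**Conclusion.** The concern holds as an omission in the analysis plan. The titre comparison between two non-randomised cohorts, matched only on age and gender, gives no role to a pre-vaccination titre that the study already needs. If post-vaccination titres are compared, a pre-vaccination difference carries into the result and can create or hide an apparent effect of metabolic syndrome.

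The omission is clear from the text, but its size is not known. At an assumed 0.5 SD imbalance, the post-only t-test rejects about 7.5–19% with no effect given baseline, and about 34% with equal mean log fold rise. At 0.25 SD under the first null the excess is small (5.6–8%), and with no imbalance there is none. These figures rest on assumed normal, uncensored log titres and assumed correlations. They should not be read as this study's actual error rate, nor as evidence that its cohorts are imbalanced. The point should be fixed before results are seen.

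**What to change.** Under Statistical Analysis, replace the unadjusted titre test with an ANCOVA for each vaccine strain: log2 Day 28 HI titre on group, with log2 pre-vaccination HI titre as covariate. Age and sex, the matching factors, may be added. In the same text:

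- Name the baseline sample: the screening tube, or Day 0 serum if volume allows. Confirm that it will be assayed by strain-specific HI.
- Give a rule for titres below 1:10.
- Report the adjusted geometric mean ratio with its 95% CI.
- State that the estimand is the response at a given baseline titre.
- As supporting analyses, report the between-group comparison of log fold rise and the unadjusted t/Wilcoxon comparison of attained titre, with baseline titres by group.

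The cost is SAP wording and one to three degrees of freedom. No new visit is needed, and seroconversion already requires a pre-vaccination HI titre. There is little precision gain if the pre/post correlation is low, and a slight loss if it is zero. Correction is incomplete if the baseline is noisy, and other confounding between the cohorts remains.

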**11.5 \* Primary Outcome(s)**

Indicate which *variable(s)* will be assessed to judge the primary specific aim. Give measurement units, if applicable.

Antibody titers and vaccine response (hemagglutinin)

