**RESEARCH LABS**

**Analyze blood sample and serum for evaluation of the immune response to influenza:****1/ Hemagglutination inhibition assay**

Determine antibody titers against each strain of influenza included in the quadrivalent 2016-2017 vaccine: A/California/7/2009 (H1N1); A/Hong Kong/4801/2014 (H3N2); B/Brisbane/60/2008(B/Victoria lineage); B/Phuket/3073/2013 (B/Yamagata lineage) as described in similar studies (10, 11).

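### HI titres are to be compared as means, with the test chosen by an unnamed normality check; a pre-set log2 analysis reported as a geometric mean ratio would supply the effect estimate that is missing

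*Combined protocol and SAP*

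**What the plan says.** Section 11.5 makes HI antibody titre part of the primary outcome, without naming a scale or summary measure. The Research Labs part of section 11.7 sets the task: "Determine antibody titers against each strain of influenza included in the quadrivalent 2016-2017 vaccine". That gives four strains, with antibody samples at screening, Day 28 and Day 90.

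The only plan for comparing titre as a quantity is under Statistical Analysis in section 11.9. It opens with "To compare the means of antibody titers between groups" and says that "a t-test at 95% significance level will be performed if the data follows a normal distribution"; "otherwise a non parametric Wilcoxon-Mann-Whitney test will be used". It does not name the normality test or its cut-off, and it does not say whether the check is made per group, pooled or per strain. No transformation, geometric mean titre, fold difference or confidence interval is given for titres. Fold changes are planned only for gene expression.

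Section 11.8 treats titre as a ratio quantity. It uses cut-offs at 1:10 and 1:40 and defines seroconversion partly by "a minimum four-fold rise in post-vaccination HI antibody titer". The proportions reaching 1:40 and seroconverting are compared separately by chi-square or Fisher test.

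**The concern.** A titre that is read in fold steps is strongly right-skewed on its natural scale. Three things follow if it is analysed untransformed.

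- A usual normality check will reject it, so the plan moves from comparing means to comparing ranks. The stated aim (means) and the test performed then differ, and a bare rank test yields a p-value with no size of difference.
- If the check happens to pass, the analysis is a t-test on arithmetic means, which a few high responders dominate.
- Because the check is unnamed, the method depends on a choice left open until the data are seen.

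With 20 per group, a non-significant p-value alone cannot separate a response that is not attenuated from a study too small to tell. An estimated fold difference with its interval can.

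**Working it through.** **Inputs from the documents.** "For a sample size of 40 participants, 20 at each group"; significance level 0.05 (two-sided assumed, because sidedness is not stated); four strains; a ratio-type definition of response.

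**Assumptions.** The documents give no SD for titres. I take log2 SD 1 to 2 as the main range and show results outside it where they matter. Titres are simulated as 10 × 2^k, with k the integer part of a normal variable and values below 10 set to 5. Doubling dilutions are inferred from the cut-offs and are not stated in the plan.

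**The plan's own figure.** The only design figure is "an effect size equal or larger than 0.56 with 0.8 power", and it concerns the chi-square test. For 40 participants, 1 degree of freedom and two-sided 0.05, the detectable effect size w at 80% power is 0.443, and power at 0.56 is 94%. So 0.56 does not reproduce on those inputs. That is a separate matter and does not bear on this point. No figure is given for the titre comparison.

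**Step 1: how often untransformed titres pass the check in both groups.**

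| Check | log2 SD 1 | 1.5 | 2 |
|---|---|---|---|
| Shapiro-Wilk | 0% | 0% | 0% |
| Lilliefors | 0% | 0% | 0% |
| D'Agostino | 6% | 2% | 0.5% |
| Kolmogorov-Smirnov, uncorrected | 16% | 22% | 13% |

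Shapiro-Wilk used 4,000 trials per setting and the others 1,500. At SD 0.75, D'Agostino passes 20%.

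**Step 2: power of each test** (20 per group, equal SDs, 4,000 trials, simulation error about 1 to 2 points).

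| log2 SD | True fold | Untransformed t | log2 t | Wilcoxon |
|---|---|---|---|---|
| 1 | 2 | 74% | 84% | 82% |
| 1.5 | 2 | 36% | 52% | 50% |
| 2 | 2 | 15% | 34% | 32% |
| 1.5 | 2.8 | 65% | 85% | 84% |
| 2 | 2.8 | 33% | 63% | 59% |

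With no true difference, Wilcoxon rejects in about 5% of trials. It falls short of the log2 t-test by about 1 to 3 points; the largest gap in the table, at SD 2 and 2.8-fold, is nearer 4 and within simulation error of 3.

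**Step 3: direction and precision of the estimate.** When the log2 SDs are equal, the ratio of arithmetic means and the ratio of geometric means estimate the same fold difference, but the arithmetic ratio is less precise. For a true two-fold difference at SD 2, the central 95% of estimates runs from 0.58 to 6.82 for arithmetic means and from 0.81 to 4.59 for geometric means. For a true halving, arithmetic means point the wrong way in about 5% (SD 1.5) and 13% (SD 2) of trials, against about 2% and 6 to 7% for geometric means.

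When the SDs differ and the geometric means are equal, the ratio of expected arithmetic means is exp[(s1² − s2²)(ln 2)²/2]:

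- 1.5 v 1: exp(1.25 × 0.2402) = 1.35
- 2 v 1.5: exp(1.75 × 0.2402) = 1.52
- 2.2 v 1.4: exp(2.88 × 0.2402) = 2.0

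In the last case, with the metabolic syndrome geometric mean truly halved, arithmetic means point the wrong way in about 40% of trials and geometric means in about 5%.

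**Step 4: would a log scale alone be enough?** No. Log2 titres are coarse and pass Shapiro-Wilk in both groups in only about 9% (SD 1), 51% (SD 1.5) and 73% (SD 2) of trials. The normality check also has to go.

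**Step 5: what the log2 analysis can detect.** At 80% power the detectable difference is (1.96 + 0.84) × SD × √(2/20) = 0.886 × SD in log2 units. That is 1.85-fold at SD 1, 2.51-fold at SD 1.5 and 3.41-fold at SD 2.

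**The case against.** The strongest reply is that the rule as written is sound as a test. If untransformed titres fail the check, the plan runs Wilcoxon, which a log transformation leaves unchanged, holds its error rate and gives up almost no power. This stands. The poor power of the untransformed t-test is a cost only in the trials that reach it.

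Second, the text never says that titres will be left untransformed; it is silent on scale. This also stands. The fair charge is that scale and check are unspecified, so an analyst could choose either after seeing the data.

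Third, a fold-based measure already exists in seroconversion. That is true, but it enters only as a proportion and gives no estimated fold difference between groups.

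A reader might infer more than this supports:

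- **That the t-test can never be used.** This holds for Shapiro-Wilk and Lilliefors, but the check is unnamed and weaker ones pass up to about 22% of trials. Different tests for different strains are possible only under those weaker checks.
- **That reported means would often contradict the truth.** The 40% figure needs much wider spread in metabolic syndrome (2.2 v 1.4), which nothing in the documents supports. Equal SDs of 1.5 and 2 give 5% and 13%. A significant Wilcoxon result with arithmetic means in the wrong direction is rare: 0.2% and 0.6% of trials at those SDs, and 4.6% even with the unequal spread.

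**Conclusion.** The point holds as a cheap improvement. The plan leaves the scale of titre and the normality check open and provides no fold difference or interval for a primary outcome that it elsewhere reads in folds. The usual result would be a valid rank test within about 1 to 3 power points of the better analysis, with no effect estimate. The less likely result, a t-test on untransformed titres, would lose about 20 points of power at SD 1.5 and 30 at SD 2 for a 2.8-fold difference.

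All sizes rest on assumed SDs and on doubling dilutions. The simulations place the control group well above the assay floor, so they do not describe a strain with many undetectable titres. The documents do not support saying that the planned test is invalid or seriously underpowered because of this rule.

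**What to change.** Replace the sentence on comparing titre means with:

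> HI titres will be analysed as log2 titre (values below 1:10 set to 1:5) by a t-test or linear model, with no preliminary normality test, using the same method for all four strains, and reported as the ratio of geometric mean titres (metabolic syndrome / control) with a 95% confidence interval; a Wilcoxon-Mann-Whitney test is a sensitivity analysis.

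The cost is one sentence, with no new data or visits. There is a small downside: setting titres below 1:10 to 1:5 is an imputation convention and would matter most for a strain with many such values. The Wilcoxon analysis covers this, because those values share the lowest rank whatever number they are given. Baseline adjustment is a separate question that this wording does not settle.
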